3.7.4 Part D Intra-subject Dose Escalation

Subjects may be allowed to re-escalate following dose reduction for AE upon resolution of AE. Please follow guidelines in [Section 3.13](#), [Section 3.14](#) and [Section 3.15](#).

3.8 Study Schematics

Figure 3-1 Trametinib Dose Escalation (Part A)

[figure not shown]
[figure not shown]

Figure 3-2 Trametinib Disease Specific Expansion (Part B)

Note: A minimum of four subjects age younger than 6 years old is required in each of the four groups.

Figure 3-3 Trametinib in Combination with Dabrafenib (Part C)

[figure not shown]

Figure 3-4 Tumor-Specific Expansion of Trametinib in Combination with Dabrafenib (Part D)

[figure not shown]
[figure not shown]

Figure 3-5 Additional Dose Exploration (Part A Extension and Part C Extension)

*Note: Part D design for 6 years to <18 years old patients is provided in [Figure 3-4](#)

3.9 Rationale

3.9.1 Rationale for Study

Despite the advances made over the past 30 years in the treatment of pediatric cancer, there remain important subpopulations within this group of patients for whom efficacious therapies have yet to be discovered. Specifically, pediatric patients with recurrent high grade gliomas, and patients with metastatic or recurrent solid tumors, continue to have a poor prognosis and lower rates of long-term survival than patients with localized or non-recurrent disease. Use of second- and third-line cytotoxic chemotherapies, even in dose-intensive regimens, has yet to yield significant impact on progression-free survival or overall survival. Therefore development of new therapeutic options for pediatric cancer patients is needed.

3.9.2 Rationale for Populations

Trametinib is FDA approved for the treatment of adults with BRAF V600 mutant-positive malignant melanoma that is unresponsive to standard therapies or for which there was no approved or curative therapy. Preliminary data from ongoing studies of trametinib in adult subjects with other advanced solid tumors (e.g., pancreatic cancer) as well as results from other MEK inhibitor clinical programs, suggest that trametinib may have beneficial effects in tumour

types beyond melanoma. Trametinib is being proposed for study in pediatric subjects with advanced solid tumors, with a focus on those that have been reported in the medical literature to potentially involve activation of the RAS/RAF signalling pathway. These include tumors positive for BRAF V600 mutation, BRAF gene duplication (e.g., juvenile pilocytic astrocytoma, low grade gliomas); NF-1 related PN; and neuroblastoma.

Part A and B of this study will focus on development of trametinib monotherapy in infants, children and adolescents with advanced or relapsed/recurrent solid tumour types that may involve activation of the RAS/RAF/MEK signalling pathway.

A concurrent study of dabrafenib in pediatric subjects with BRAF V600 mutation positive tumors is ongoing. Recent data from adult studies indicate that the combination of trametinib with dabrafenib is well tolerated and may provide more benefit to subjects with BRAF V600 mutation in tumors. Therefore, subjects with BRAF V600 mutation in tumors may be enrolled.

Part C and D of this study will focus on development of trametinib and dabrafenib combination therapy in children and adolescents with BRAF V600 mutation positive tumors.

3.9.3 Rationale for Dose

3.9.3.1 Trametinib

The targeted dose and schedule of trametinib is based on the adult clinical dose and schedule required to achieve therapeutic benefit in BRAF mutant melanoma. In adults, the mean (range) AUC(0- τ) following repeat dosing of 1 and 2 mg once daily was 175 ng•hr/mL (107-243 ng•hr/mL) and 360 ng•hr/mL (204-536ng•hr/mL), respectively. The mean (range) C τ following repeat dosing of both the 1 and 2 mg once daily doses were 13.8 (n=2, 8.44 and 19.1 ng/mL) and 12.1 ng/mL (n=13, 8.3-16.9 ng/mL, CV=19%, 95%CI=10.86-13.4), respectively. The lowest C τ concentration associated with an objective response was approximately 7 ng/mL, where 1 complete response (CR) (1 mg dose) and 1 partial response (PR) (0.5 mg dose) were observed of 12 subjects with C τ of 7 ng/mL.

Given the safety and tolerability observed at the adult dose of 2 mg once daily and the variability associated with the mean adult trough concentration (95%CI=10.86-13.4), therapeutic benefit in pediatric subjects may be achieved by attaining trough concentration at steady state (day 15 C τ \geq 10 ng/mL) that is similar to those achieved in adults at the recommended dose. In the absence of DLT, if the PK exposure (C τ) is significantly lower than those achieved in adults, higher doses for subsequent cohorts may be modified in a protocol amendment in order to achieve PK target during dose escalation.

The starting dose in the pediatric population will be based on 1 mg as given to average 80 kg adult subject (0.0125 mg/kg) which is 50% of the recommended and FDA approved dose in adults. Steady state trough concentration (Cycle 1 Day 15 C τ (trough) data for trametinib from adults will be compared to PK data in the pediatric subjects and will guide pediatric dose recommendations. Exposure and Day 15 C τ will be assessed in-stream during the study. PK sampling at day 15, modelling and simulation will allow prediction of trametinib dosage regimens for children that will deliver target trametinib steady-state concentrations and exposure similar to adults.

Three dose levels are planned in pediatric subjects. In the absence of DLT, if the PK exposure is significantly lower than those achieved in adults, higher doses for subsequent cohorts may be modified in a protocol amendment in order to achieve PK target during dose escalation.

Since the approval and implementation of Amendment 3, the dose of 0.04 mg/kg/day was found to result in DLTs and 0.025 mg/kg/day was established as the RP2D of trametinib in Parts B and C based on safety and tolerability. Based on preliminary trametinib PK analysis in patients at the selected dose of 0.025 mg/kg in Parts A, B and C (data cut-off 31-Oct-2016), the median trametinib C_{tr} was 8.2 ng/mL in patients < 6 years (Table 3-3). Due to this trend of lower trametinib exposure in patients < 6 years, an intermediate dose of 0.032 mg/kg/day may achieve exposures that are similar to those in adults. This dose will be explored as single agent first. If safety and tolerability permit, this dose will be tested in combination with dabrafenib.

Table 3-3 Median trametinib PK (Day 15) by age groups

Age Range	Dose (mg/kg)	N	C_{trough} (ng/mL)
< 6 years	0.025	22	8.2
6-17 years	0.025	30	11.7

Age-related anatomical and physiological changes occur in the first 6 months to 24 months that may affect drug absorption and disposition. This study will evaluate appropriateness of weight based dosing across three age groups; those less than 2 years of age, those 2 years of age to 12 years of age (inclusive), and those over 12 years of age up to <18 years of age.

3.9.3.2 Starting dose for Part C, Trametinib in Combination with Dabrafenib

In adults the recommended dose of trametinib in combination with dabrafenib is the full adult monotherapy dose of each: trametinib 2 mg PO daily and dabrafenib 150 mg PO twice daily. In the context of this clinical trial, the trametinib dose administered in Part C will be the trametinib monotherapy RP2D from Part A. The monotherapy RP2D of dabrafenib in children was established on a separate trial (BRF116013). The following RP2D doses were determined for dabrafenib:

- < 12 years old subjects: 5.25 mg/kg/day dabrafenib administered orally, divided into two equal doses
- \geq 12 years old subjects: 4.5 mg/kg/day dabrafenib administered orally, divided into two equal doses

For the evaluation of combination therapy on this trial, the starting dose of dabrafenib (Dose Level 1) will be 50% of the RP2D, divided into two equal doses. If tolerated a single dose escalation to the full dabrafenib RP2D (Dose Level 2) will be evaluated. If dose levels proposed are not well tolerated, intermediate dose levels of dabrafenib and/or trametinib may be evaluated if warranted.

Table 3-4 Recommended dabrafenib dose levels

Dose Level	Dabrafenib		Trametinib
	< 12 years	≥ 12 years	All ages
1 (Starting dose)	2.63 mg/kg/d	2.25 mg/kg/d	RP2D
2	5.25 mg/kg/d	4.5 mg/kg/d	RP2D

The RP2D for trametinib monotherapy determined in Part A extension for patients aged 1 month to < 6 years (either 0.025 mg/kg/day or 0.032mg/kg/day) along with full dabrafenib RP2D will be the starting dose for Part C extension patients (aged 12 months to <6 years).

3.9.3.3 Starting dose for Part D, Trametinib in Combination with Dabrafenib

Based on safety, tolerability and PK, the dose of trametinib and dabrafenib in patients 6 years to <18 years will be the RP2D (0.025mg/kg/day trametinib and full RP2D of dabrafenib) already determined from Part C. For patients <6 years old, the trametinib dose will be determined from Part C extension (or Part A extension) and will be either 0.025 mg/kg/day or 0.032 mg/kg/day. The selected dose of trametinib will then be combined with the full RP2D of dabrafenib (100% of monotherapy dose) in patients under 6 years of age, just as in other age groups. Patients who are 6 to < 18 years old will start enrolling in Part D in parallel with the testing of the additional dose level of trametinib in Part A extension, (patients aged 1 month to < 6 years) and then in Part C extension, (patients aged 12 months to <6 years).

The safety of the combination of trametinib and full dose dabrafenib has been confirmed in adults and pediatrics. Similar to other age groups, the dose of 0.025 mg/kg/day trametinib was tolerated with full dose dabrafenib (5.25 mg/kg/day) in patients under 6 years of age in Part C. The dose of 0.032 mg/kg/day trametinib will be brought forward into Part D for patients under 6 years of age only if it is shown to be safe when given as monotherapy in Part A extension and as combination therapy in Part C extension.

3.9.4 Rationale for Endpoints

This study will be the first administration of trametinib to pediatric subjects. Safety parameters will be carefully and systematically monitored.

Part A: The expectation is that a PK endpoint will help define a dose that will provide an efficacious exposure in pediatric subjects without the need to reach maximum toxicity levels. In the absence of DLT in this pediatric study, a PK target endpoint will be used as the primary endpoint for dose determination. In adults, there is minimal intersubject variability in the steady state C_{τ} (CV 19%, 95%CI=10.86-13.4), and responses were observed at exposures as low as $C_{\tau} = 7$ ng/mL in subjects with melanoma, while efficacy has been clearly identified at known plasma levels of study drug (≥ 10 ng/mL trough) which were well tolerated. However, safety will be carefully reviewed and DLT definitions are incorporated in the protocol should safety in pediatric subjects differ from those in adult subjects following treatment with trametinib.

Part A extension: Based on preliminary PK data from Parts A, B and C, there was a trend for lower trametinib exposure in patients < 6 years old. An intermediate dose that is between the RP2D established in Part A and the higher dose that exceeded MTD will be explored. Safety, tolerability and PK are the primary endpoints of this part of the study.

Part B: The RP2D established in Part A and verified by age cohorts (1 month to <2 years, 2 years to ≤ 12 years and >12 years) will be administered in Part B. Safety, tolerability and preliminary activity assessed by investigator are the primary endpoints of this part of the study..

Part C: Subjects will be monitored for DLT and toxicity using the same DLT criteria as in Part A. Safety, tolerability and preliminary activity are the primary endpoints of this part of the study. In the absence of DLT, dose escalation will not exceed the trametinib monotherapy RP2D in combination with the dabrafenib monotherapy RP2D.

Part C extension: If Part A extension indicates trametinib 0.032mg/kg/day is tolerated in patients < 6 years old, the same trametinib dose will be explored in Part C extension with full dabrafenib RP2D. Safety, tolerability and PK are the primary endpoints of this part of the study.

Part D: Safety and tolerability are the primary endpoints of this part of the study.

3.10 Study Treatment

3.10.1 Treatment Assignment

Subjects will be identified by a unique subject number that will remain consistent for the duration of the study. Each site will be given a subject number range. These ranges and details regarding assignment of subject numbers can be found in the SPM.

Treatment will not be randomized; nonetheless, each subject will be assigned a randomization number as described in SPM.

At the time of enrollment, subjects will be assigned to one part of the study designated Part A or Part B or Part C or Part D. Individual subjects will participate in the specified part of the study, however, data analysis may combine parts of the study. For example, all subjects treated at the trametinib RP2D dose in Part A will contribute to age expansion in Part A of the study. Response evaluations in subjects in Part A of the study at the RP2D will be considered in analysis of Part B for specific disease cohorts.

3.11 Dosage and Administration of Study Treatments

3.11.1 Trametinib

Please note that study drug dispensed to subjects in the original container should not be repackaged without explicit permission from the Sponsor. Trametinib is administered orally once daily under fasting conditions, either 1 hr before or 2 hr after a meal. Subjects should be encouraged to take trametinib approximately 24 hours apart at the same time each day. Dose levels are provided in [Section 3.2.1](#).

Ideally, patients will take the trametinib study drug in the morning up through the PK day. After the PK day, the patient may change to evening dosing, if they prefer. If the patient is on an evening dosing regimen as they enter the PK testing period, the evening dose prior to the PK day SHOULD BE taken by the patient. In all cases, the timing of the dose prior to the PK sampling must be maintained and recorded accurately.

For trametinib tablets, it is recommended that subjects drink approximately 4 to 6 mL of water/kg body weight with each dose.

Trametinib pediatric oral solution formulation will be administered with a graduated syringe. It is recommended that subjects drink 4 to 6 mL of water/kg body weight following dosing.

A dosing nomogram (see [Appendix 2](#)) based on weight and dose level will be used to prescribe trametinib to minimize inter-subject dosing variability. If a subject vomits after taking study medication, the subject should be instructed not to retake the dose and should take the next scheduled dose. If a subject misses a dose, subject should not double the next regularly scheduled dose. However, subject can take the missed dose immediately if the next scheduled dose is at least 12 hr later. Subject should take the next dose at its usual time.

The total daily trametinib dose should not exceed the adult dose (2mg) in any subject.

Refer to [Section 3.13](#), [Section 3.14](#) and [Section 3.15](#) for dose modifications for toxicity.

3.11.3 Meals and Dietary Restrictions

All subjects will fast except for water ad libitum for 2 hr prior and 1 hr following administration of trametinib and/or dabrafenib in either formulations. Data from the adult trametinib food effect study (MEK113709) demonstrated that administration of trametinib with a high-fat, high-calorie meal resulted in an approximate 70% decrease in C_{max} and 10-24% decrease in AUC compared to administration under fasting conditions. Data from the adult dabrafenib food effect study (BRF113468) demonstrated that administration of dabrafenib following a high-fat, high-calorie meal resulted in an approximate 30% decrease in exposure and 50% decrease in C_{max} compared to administration under fasting conditions.

- If it is not possible for a subject to tolerate the fasting conditions noted above, trametinib and/or dabrafenib can be administered with a small non-fat meal (e.g., small amount of apple juice/sauce, a piece of dry toast). Children that are breastfeeding may continue to breast feed on demand. If child is breast fed during collection of PK samples the time of breastfeeding should be recorded.
- Avoid administration with high-fat or high calorie food or beverages, examples milk, beverages containing dairy products or high protein beverages or supplements for 2 hr prior and 1 hr following administration of trametinib and/or dabrafenib in either formulation.

3.11.4 Blinding

This is an open-label study.

3.12 Safety Management Guidelines

3.12.1 Liver Chemistry Stopping Criteria

Liver chemistry threshold stopping criteria have been designed to assure subject safety and to evaluate liver event etiology during administration of study treatment(s) and the follow-up period. Upper limit of normal (ULN) for ALT in this study will be 45 U/L. **Study treatment(s) will be stopped if any of the following liver chemistry stopping criteria is/are met:**

1. ALT ≥ 3 times upper limit of normal (ULN) and bilirubin ≥ 2 times ULN (or ALT ≥ 3 times ULN and international normalization ratio [INR] > 1.5)
 - NOTE: Serum bilirubin fractionation should be performed if testing is available. If fractionation is unavailable, urinary bilirubin is to be measured via dipstick (a measurement of direct bilirubin, which would suggest liver injury).
2. ALT ≥ 5 times ULN.
3. ALT ≥ 3 times ULN if associated with the appearance or worsening of rash or hepatitis symptoms (fatigue, nausea, vomiting, right upper quadrant pain or tenderness, or jaundice) or hypersensitivity (such as fever, rash or eosinophilia).
4. ALT ≥ 3 times ULN persists for ≥ 4 weeks.

5. ALT ≥ 3 times ULN and cannot be monitored weekly for 4 weeks.

Subjects with ALT ≥ 3 times ULN **and** < 5 times ULN **and** bilirubin < 2 times ULN, who do not exhibit hepatitis symptoms or rash, can continue study treatment(s) as long as they can be monitored weekly for 4 weeks. See following section for details on weekly follow-up procedures for these subjects.

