3.12.1.1 Liver Chemistry Follow-up Procedures

The procedures listed below are to be followed if a subject meets the liver chemistry stopping criteria 1 through 5 defined in [Section 3.12.1](#):

- Immediately discontinue study treatment(s).
- Notify the Medical Lead within 24 hr of learning of the abnormality to confirm the subject's study treatment(s) cessation and follow-up.
- Complete the "Safety Follow-Up Procedures" listed below.
- Complete the liver event electronic case report forms (eCRFs). If the event also meets the criteria of a SAE (see [Section 8.2](#)), the SAE data collection tool will be completed separately with the relevant details.
- Upon completion of the safety follow-up permanently withdraw the subject from the study and do not rechallenge with study treatment(s).

Safety Follow-Up Procedures for subjects with ALT ≥ 3 times ULN:

- Monitor subjects **weekly** until liver chemistries (ALT, aspartate aminotransferase [AST], alkaline phosphatase [ALP], and bilirubin) resolve, stabilize or return to within baseline values.

Safety Follow-Up Procedures for subjects meeting stopping criterion 1 (ALT ≥ 3 times ULN and bilirubin ≥ 2 times ULN [or ALT ≥ 3 times ULN and INR > 1.5]):

- **This event is considered an SAE** (see [Section 8.2](#)). Serum bilirubin fractionation should be performed if testing is available. If fractionation is unavailable, urinary bilirubin is to be measured via dipstick (a measurement of direct bilirubin, which would suggest liver injury).
- Make every reasonable attempt to have subjects return to the clinic within 24 hr for repeat liver chemistries, additional testing, and close monitoring (with specialist or hepatology consultation recommended).
- Monitor subjects **twice weekly** until liver chemistries (ALT, AST, ALP, bilirubin) resolve, stabilize or return to within baseline values.
- In addition, every attempt should be made to carry out the liver event follow-up assessments described in [Section 3.12.1.2](#).

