3.12.1.2 Liver Chemistry Testing Procedures

For subjects meeting any of the liver chemistry stopping criteria in [Section 3.12.1](#), make every attempt to carry out the liver event follow-up assessments described below. Laboratory tests for

liver events will be performed at the central laboratory. Additional information can be found in the lab manual and SPM.

- Viral hepatitis serology, including:
 - Hepatitis A IgM antibody
 - Hepatitis B surface antigen and Hepatitis B Core Antibody (IgM)
 - Hepatitis C RNA
 - Cytomegalovirus IgM antibody
 - Epstein-Barr viral capsid antigen IgM antibody (or if unavailable, then obtain heterophile antibody or monospot testing)
- Blood sample for pharmacokinetic (PK) analysis, obtained within 20 days of the last dose of study treatment(s). Record the date and time of the PK blood sample draw and the date and time of the last dose of study treatment(s) prior the blood sample draw on the eCRF. If the date or time of the last dose is unclear, provide the subject's best approximation. If the date or time of the last dose cannot be approximated, or if a PK sample cannot be collected within the 20-day period following the last dose, do not obtain a PK sample. Instructions for sample handling and shipping are found in the Study Procedures Manual (SPM).
- Serum creatine phosphokinase (CPK) and lactate dehydrogenase (LDH).
- Fractionate bilirubin, if total bilirubin ≥ 2 X upper limit of normal (ULN).
- Obtain a complete blood count (CBC) with differential to assess eosinophilia.
- Record the appearance or worsening of clinical symptoms indicative of hepatitis or hypersensitivity, such as fatigue, nausea, vomiting, right upper quadrant pain or tenderness, fever, rash or eosinophilia as relevant on the AE eCRF.
- Record the use of concomitant medications, including acetaminophen, herbal remedies or any other over the counter (OTC) medications, or any putative hepatotoxins, on the concomitant medication eCRF.
- Record alcohol use on the liver event alcohol intake eCRF.

Every attempt should be made to obtain the following assessments for subjects with ALT ≥ 3 X ULN and bilirubin ≥ 2 X ULN (>35% direct). These assessments are optional for other abnormal liver chemistries:

- Anti-nuclear antibody, anti-smooth muscle antibody, and Type 1 anti-liver kidney microsomal antibodies.
- Liver imaging (ultrasound, MRI or CT) to evaluate liver disease.

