- All events of possible study treatment-induced liver injury with hyperbilirubinemia defined as alanine aminotransferase (ALT) ≥ 3 times ULN and bilirubin ≥ 2 times ULN ($>35\%$ direct) (or ALT ≥ 3 times ULN and international normalization ratio (INR) >1.5 , if INR is measured) or termed ‘Hy’s Law’ events (INR measurement is not required and the threshold value stated will not apply to subjects receiving anticoagulants).

NOTE: Bilirubin fractionation is performed if testing is available. If testing is not available, record presence of detectable urinary bilirubin on dipstick indicating direct bilirubin elevations and suggesting liver injury. If testing is unavailable and a subject meets the criterion of total bilirubin ≥ 2 times ULN, then the event is still reported as a SAE. If INR is obtained, include values on the SAE form. INR elevations >1.5 suggest severe liver injury.

- Any new primary malignancy with a histology different from the primary tumor.
- LVEF that meets stopping criteria.
- RPED or RVO.

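### Liver stopping criterion 1 applies INR above 1.5 to every subject, while Section 8.2 and Table 8-1 exempt subjects on anticoagulants from the same threshold

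*Protocol*

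**What the plan says.** **Stopping rule.** Section 3.12.1 fixes the ALT upper limit of normal (ULN) at 45 U/L and makes stopping mandatory if any one of five criteria is met. Criterion 1 is ALT ≥3×ULN with bilirubin ≥2×ULN or, alternatively, with INR >1.5 ("times ULN and international normalization ratio [INR"). It makes no exception for anticoagulated subjects.

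**Consequence.** Section 3.12.1.1 applies to all five criteria: immediate discontinuation, completion of the liver event eCRF, and then "Upon completion of the safety follow-up permanently withdraw the subject from the study and do not rechallenge with study treatment(s". Section 6.3 adds that a subject who has permanently discontinued may not be retreated, and Section 3.1 rules out waivers.

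**SAE status.** An early bullet in 3.12.1.1 makes it conditional ("If the event also meets the criteria of a SAE"). The block on criterion 1 then restates the ALT and INR pair and says "This event is considered an SAE", pointing to Section 8.2.

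**Exemption.** Section 8.2 lists the same ALT and INR pair as a protocol-specific SAE but adds that "INR measurement is not required and the threshold value stated will not apply to subjects receiving anticoagulants". Table 8-1 footnote c repeats this for reporting.

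**Who is in the trial.** Sections 5.2.1.4 and 5.2.1.5 admit anticoagulated subjects to Parts C and D if their INR is in the therapeutic range. Section 9.1 permits anticoagulants such as warfarin, Section 9.2.1 prohibits nothing in Parts A and B, and Section 9.3 allows therapeutic warfarin in Parts C and D with Medical Lead approval.

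**The concern.** An INR raised by an anticoagulant does not by itself show that the liver is failing. Two places in the protocol recognise this and switch the threshold off for such subjects. The two places that decide whether the child stays on treatment do not.

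At stake is permanent loss of study treatment for a child whose disease is relapsed, refractory or without a curative option (Section 5.2.1.1), after an ALT rise that would otherwise be handled by weekly monitoring.

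The INR limb also bears mainly on the exempted group. INR is not among the laboratory tests in Table 7-6 and Section 8.2 does not require it, whereas Sections 9.1 and 9.3 call for INR monitoring in warfarin users. The subjects most likely to have an on-treatment INR are those to whom Section 8.2 says the threshold does not apply.

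**Working it through.** The plan gives no figure to reproduce. The check is a side-by-side reading, with simple arithmetic on the ALT limits.

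**1. ALT band.** With ULN = 45 U/L (Section 3.12.1):
- lower limit, criterion 1: 3 × 45 = 135 U/L
- criterion 2: 5 × 45 = 225 U/L, where treatment stops whatever the INR

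The exemption can therefore change the outcome only for ALT from 135 to below 225 U/L.

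**2. Remove every other route to stopping.** Within that band the INR limb decides alone only if:
- bilirubin is below 2×ULN (otherwise the bilirubin limb of criterion 1 applies)
- there is no rash, hepatitis symptom or hypersensitivity sign (criterion 3)
- the elevation has lasted less than 4 weeks (criterion 4)
- weekly monitoring for 4 weeks is possible (criterion 5)

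**3. Worked case.** Child on warfarin, ALT 150 U/L (150 / 45 = 3.3×ULN), bilirubin 1.0×ULN, no symptoms, under 4 weeks, weekly monitoring arranged. INR is 2.0; this value is assumed, since the protocol states no therapeutic range.

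| Place in protocol | Instruction for this child |
|---|---|
| 3.12.1, criterion 1 | Met: stop treatment |
| 3.12.1, criteria 2 to 5 | Not met |
| 3.12.1.1 | Liver event eCRF, permanent withdrawal, no rechallenge; event is an SAE, see 8.2 |
| 8.2, protocol-specific SAE | INR threshold does not apply: not this SAE |
| Table 8-1 with footnote c | Falls to the row for ALT 3 to <5×ULN and bilirubin <2×ULN: notify within 24 hr, no Liver Event eCRF unless the rise persists for 4 weeks or weekly monitoring is impossible |
| 3.12.1, closing paragraph, if the INR limb is set aside | Subjects "who do not exhibit hepatitis symptoms or rash, can continue study treatment(s) as long as they can be monitored weekly for 4 weeks" |

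The instructions differ on three points: SAE or not under the protocol-specific item, liver eCRF or not, and, if the exemption is carried to the stopping rule, withdrawal or continuation.

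**4. How often.** If the therapeutic target lies above 1.5, every child on target within the conditions of steps 1 and 2 is withdrawn. If it lies at or below 1.5, only children whose INR overshoots are. The protocol gives no count of subjects on anticoagulants, so no rate can be computed.

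**The case against.** **Different sections, different purposes.** Section 8.2 and Table 8-1 govern SAE definition and reporting; Section 3.12.1 governs stopping. A stopping rule may be broader than a reporting rule, and a cautious stop is defensible when ALT is ≥3×ULN and INR can no longer show whether liver function is preserved. Part of this stands: neither exemption mentions stopping, so the text does not prove that the sponsor meant it to reach criterion 1. It is not a full answer, because 3.12.1.1 declares every criterion 1 event an SAE and cites 8.2, whose own item excludes this child. The pointer sends the reader to the exemption without saying which text governs.

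**Follow-up is not empty.** Section 3.12.1.1 asks for return within 24 hr, repeat chemistries, additional testing and a recommended specialist consultation, and 3.12.1.2 requires concomitant medications to be recorded. These help attribution. None reverses withdrawal, and the Medical Lead contact ("Notify the Medical Lead within 24 hr of learning of the abnormality to confirm the") serves to confirm cessation and follow-up.

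**Stronger readings a reader might infer, which the documents do not support:**
- *That the bilirubin limb is sound and the INR limb is not, because bilirubin is fractionated afterwards* ("Fractionate bilirubin, if total bilirubin"). Fractionation follows the stop, and nothing lets its result undo withdrawal. Both limbs are equally final.
- *That the closing paragraph of 3.12.1 contradicts criterion 1 because it names no INR limit.* The mandatory rule that any one criterion suffices governs that paragraph.
- *That the 37% fall in warfarin exposure on dabrafenib in Section 9.3 measures the risk of INR overshoot.* It is an exposure figure, not INR, and the same section calls for close PT/INR monitoring and possible warfarin dose adjustment.

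**Conclusion.** The inconsistency is real and minor. That the exemption is absent from 3.12.1 and 3.12.1.1 and present in 8.2 and footnote c is certain from the text. That the absence is an oversight is a reasonable reading but not proven.

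The effect is confined to anticoagulated subjects who meet every condition in steps 1 and 2 of the working and have INR above 1.5. For them the text as written ends treatment for good, possibly for an anticoagulant effect. The number is unknown, probably very small and possibly zero; Amendment 9 states that all cohorts have completed enrolment. The SAE mismatch errs towards over-reporting and is the lesser harm. No endpoint is affected.

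The conclusion assumes that some anticoagulated subjects have an INR above 1.5 on treatment. The protocol gives no therapeutic range, but it makes a separate allowance for these subjects beside its PT/INR limit of 1.3×ULN, which implies INR values above that limit.

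**What to change.** Add to criterion 1 in Section 3.12.1, and to its restatement in 3.12.1.1, that the INR threshold does not apply to subjects receiving anticoagulants, matching Section 8.2 and Table 8-1 footnote c. This also aligns the SAE sentence in 3.12.1.1, since an event resting only on INR in such a subject would no longer be a criterion 1 event. The bilirubin limb and criteria 2 to 5 stay as they are and still apply to these subjects.

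The cost is wording only: no change to visits, samples or enrolment. The small downside is that INR no longer triggers a stop in anticoagulated subjects, so their liver protection rests on the bilirubin limb, criteria 2 to 5 and weekly monitoring.
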